#### Handling of study drop-out:

Based on data from a prior study (the TEA trial) of 113 patients with first-episode psychosis aged 12-17 years conducted in our CAMHS in the period 2010-2014 we have evaluated the expected study drop-out in the OPUS YOUNG trial. The TEA trial compared the beneficial and harmful effects of two antipsychotics, aripiprazole versus quetiapine, in a 12-week study. The drop-out rate (lost to follow-up assessments at week-2, week-4 or week-12) was 14% and 10%, respectively. In the TEA trial missing data was handled by intention-to-treat-analysis and multiple imputations [123]. In the OPUS YOUNG study, including an identical group of participants, we expect a drop-out rate of approximately 10%. We expect that the combination of pharmacological and psychosocial treatment in both intervention arms will motivate the patient and family to adhere to treatment. Furthermore, even though the drop-out rate for the two-year adult OPUS study was approximately 30%, our experience from the clinic is that parents intensively support young patients to adhere to treatment and support continued participation in clinical trials.

As we scientifically and ethically find it important to strive to include the most exact needed number of participants possible, not too few (risk of loss of statistical power), not to many (risk of burdening too many patients with engagement in a RCT) we will handle missing data as a result of study drop-out by performing intention-to-treat analysis with multiple imputation of missing data [124]. See also section on statistical analysis below.

#### Power calculation for secondary outcome measures

For secondary outcomes, we have performed power calculations on the most relevant secondary outcome measures. Based on the results of the power calculations the measures SAPS, SANS, CSQ, and KIDSCREEN-10, were selected as secondary outcomes.

#### SAPS, SANS

We are planning a trial with a minimum of 284 participants randomized 1:1. In a previous study, the response within each intervention group was normally distributed with a SD of 1.4 (SAPS) and 1.2 (SANS) points. If the true difference in the experimental group (OPUS YOUNG) and control group (TAU) for both SAPS and SANS is a mean of 0.4 points [125] with a standard deviation of 1.4/1.2 points, we will be able to reject the null hypothesis that the population means of the experimental and control groups are equal with probability (power) of 80%. The type I error probability associated with this test of this null hypothesis is 5%.

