#### KIDSCREEN-10

We are planning a trial with a minimum of 284 participants randomised 1:1. If the true difference in the experimental group (OPUS YOUNG) and control group (TAU) is a mean of 5 points and with

an expected standard deviation of 10 points [126], we will be able to reject the null hypothesis that the population means of the experimental and control groups are equal with probability (power) of 99%. The type I error probability associated with this test of this null hypothesis is 5%.

OUTCOME	MIREDIF	SD	Ν	Power
Primary				
PSP	5.0	13	2*142	90%
Secondary				
SAPS	0.4	1.2	2*142	80%
SANS	0.4	1.2	2*142	80%
CSQ	3.09	4.45	2*142	99%
KIDSCREEN-10	5	10	2*142	99%

Table 4 Power calculation

Notes: Minimal relevant difference of outcome measure (MIREDIF), Standard Derivation (SD), Number of cases (N)

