#### Statistical analyses

The analyses will be according to intention-to-treat with two-sided tests. Missing data will be handled by multiple imputations. The primary outcome measure, as other continuous outcome measures, will be analysed with mixed model analysis with repeated measurements with unstructured variance matrix, using the mixed model command in SPSS. This approach assumes that the distribution of missing data can be estimated from the information from previous assessments and from information about other participant cases in the database. The condition for using this method is the assumption that data are missing at random or missing completely at random when taking into consideration the information extracted from baseline assessments and information about the other participants in the database. In this model, baseline values of the scales are included. All tests will be two-tailed. The threshold for the significance level will be set at p<0.05. For evaluation of the dichotomous outcome measures, we will use multiple multivariate imputations, using all other covariates to impute a distribution of missing values. The dichotomous outcomes will be analysed with logistic regression analyses. Variables included as covariates will be the same as those included in analyses of continuous measures. Similar to the repeated measurement, the condition for using multiple imputations requires that data are missing at random or missing completely at random, when taking into consideration the information extracted from baseline interviews and information about the other patients in the database. Analysis will be based on intention-to-treat principles. Data from all patients will be included in the group to which random assignment is made, regardless of intervention received.

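### The 80% power stated for SAPS does not follow from the text's SD of 1.4, which gives 67%; Table 4 shows 80% with an SD of 1.2

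*Protocol*

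**What the plan says.** In the Protocol section on SAPS and SANS, the planning values come from an earlier trial: "In a previous study, the response within each intervention group was normally distributed with a SD of 1.4 (SAPS) and 1.2 (SANS) points". The size is fixed by "We are planning a trial with a minimum of 284 participants randomized 1:1". The assumed difference "for both SAPS and SANS is a mean of 0.4 points", and the power sentence repeats the two SDs: "with a standard deviation of 1.4/1.2 points". One power of 80% is then given for both scales at a 5% type I error.

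Table 4, at the end of the KIDSCREEN-10 section, gives difference, SD, sample size and power for each outcome. Its SAPS row reads "SAPS 0.4 1.2 2*142 80" (per cent). The SANS row carries the same four values.

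Two other places matter. The Statistical analyses section says "All tests will be two-tailed". The introduction to the secondary power calculations says "Based on the results of the power calculations the measures SAPS, SANS, CSQ, and KIDSCREEN-10, were selected as secondary outcomes".

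**The concern.** Two scales with different SDs, the same assumed difference and the same sample size cannot have the same power. The text gives SAPS the larger SD and still claims 80% for both. Table 4 removes the discrepancy by giving SAPS the SANS value.

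Positive symptoms are part of hypothesis 2, and the protocol says the secondary outcomes were selected on the results of these calculations. If the larger SD is correct, a null SAPS result would be read against a power that the trial does not have.

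**Working it through.** **Inputs.** Difference 0.4 (SAPS, SANS section and Table 4). SD 1.4 for SAPS and 1.2 for SANS (text), or 1.2 for both (Table 4). 142 per arm (284 randomised 1:1). Two-sided 5%, so z = 1.960.

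**Formula.** For two means with a common SD and n per arm, SE = SD × √(2/n) and power = Φ(difference/SE − 1.960). This is the power form of the sample-size formula that the protocol gives for PSP.

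**The plan's own figures first.**

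- PSP (difference 5, SD 13): 90.0%, stated 90%.
- KIDSCREEN-10 (5, SD 10): 98.8%, stated 99%.
- CSQ (3.09, SD 4.45): above 99.9%, stated 99%.
- SANS (0.4, SD 1.2): SE = 1.2 × √(2/142) = 0.1424; 0.4/0.1424 = 2.809; Φ(2.809 − 1.960) = 80.2%, stated 80%. The t-test version gives 79.9%.

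The method matches the sponsor's: three figures reproduce, and CSQ is understated.

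**SAPS at the text's SD.** SE = 1.4 × √(2/142) = 0.1661; 0.4/0.1661 = 2.407; Φ(2.407 − 1.960) = 67.3%. The t-test version gives 67.0%. The stated 80% is about 13 percentage points too high.

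**What 80% would require at SD 1.4.**

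- Detectable difference with 142 per arm: (1.960 + 0.842) × 0.1661 = 0.47 points.
- Sample size for 0.4 points: 4 × (1.960 + 0.842)² × (1.4/0.4)² ≈ 385, which means 193 per arm (386 in total). The plan is for 284 to 304.

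**Other readings at SD 1.4, difference 0.4.**

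| Reading | Power |
|---|---|
| 152 per arm (planned maximum), two-sided | 70.2% |
| 128 per arm (142 less the expected 10% drop-out), two-sided | 62.8% |
| 142 per arm, one-sided 5% | 77.7% |
| 1.4 and 1.2 read as the SDs of the two arms, 142 per arm | 73.4% |
| 152 per arm and one-sided 5% | 80.1% |

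Only the last row reaches 80%. It conflicts with the 284 participants on which the statement rests and with the two-tailed tests.

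**The case against.** The strongest objection is that the 80% may be correct. The earlier study is not reproduced in the protocol. If its SAPS SD was 1.2, the error lies in the text's SD and the stated power stands. The text gives 1.4 twice and ties it to that study, which favours 1.4 but does not prove it. So the contradiction is established, and the 67% is conditional on the SD.

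A second objection is that the planned analysis is a mixed model that includes baseline values, which can gain precision over a plain comparison of means. With an assumed baseline-outcome correlation r, the effective SD is 1.4 × √(1 − r²). Power is then about 71% at r = 0.3 and 79% at r = 0.5. This bears on the power of the eventual analysis. It does not explain the stated figure, because the power section gives no correlation and describes a simple comparison with within-group SDs. The same adjustment would also raise SANS to about 90% at r = 0.5 (effective SD 1.2 × √0.75 = 1.04), yet one figure of 80% is given for both scales.

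Third, SAPS is a secondary outcome. PSP alone sets the sample size, and its power reproduces. The protocol states no power threshold for selecting secondary outcomes, so nothing shows that 67% would have excluded SAPS. A null result will in any case be judged mainly by its confidence interval. All of this stands and limits the consequence, but it does not remove the error.

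**Conclusion.** The SAPS power statement is wrong as written. Its inputs (0.4 points, SD 1.4, 142 per arm, two-sided 5%) give 67%, not 80%, and Table 4 contradicts the text on the SD. No design feature stated in the protocol recovers 80% at SD 1.4.

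The 67% assumes an unadjusted comparison of two means, as the power section describes, with no loss to follow-up. If 1.4 is the source SD, the chance of missing a true 0.4-point difference is 33% (100 − 67), against the 20% implied by the protocol. If 1.2 is the source SD, the power stands and only the text's SD is wrong. The primary outcome's sample size is unaffected in either case.

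**What to change.** Check the SAPS SD against the earlier study and make the text and Table 4 agree.

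- **If it is 1.4:** set the SAPS row of Table 4 to SD 1.4 and power 67%. In the text, state power separately for SAPS (67%) and SANS (80%), and say that for SAPS 80% power holds for a difference of 0.47 points.
- **If it is 1.2:** correct the SAPS SD at both places in the text. The 80% then stands.

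If the sponsor wants to rely on baseline adjustment, the assumed correlation should be stated and the SANS figure recalculated on the same basis.

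The cost is a few figures in one section and one table row. No extra patients are needed and the analysis does not change. If 1.4 is right, the price is a less favourable stated power for SAPS.

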#### CSQ

We are planning a trial with a minimum of 284 participants randomised 1:1. In a previous study the response within each intervention group was normally distributed with an SD of 4.45 points. If the true difference in the experimental group (OPUS YOUNG) and control group (TAU) is a mean of 3.09 points [125] with a standard deviation of 4.45 points, we will be able to reject the null hypothesis that the population means of the experimental and control groups are equal with probability (power) of 99%. The type I error probability associated with this test of this null hypothesis is 5%.

#### KIDSCREEN-10

We are planning a trial with a minimum of 284 participants randomised 1:1. If the true difference in the experimental group (OPUS YOUNG) and control group (TAU) is a mean of 5 points and with

an expected standard deviation of 10 points [126], we will be able to reject the null hypothesis that the population means of the experimental and control groups are equal with probability (power) of 99%. The type I error probability associated with this test of this null hypothesis is 5%.

OUTCOME	MIREDIF	SD	Ν	Power
Primary				
PSP	5.0	13	2*142	90%
Secondary				
SAPS	0.4	1.2	2*142	80%
SANS	0.4	1.2	2*142	80%
CSQ	3.09	4.45	2*142	99%
KIDSCREEN-10	5	10	2*142	99%

Table 4 Power calculation

Notes: Minimal relevant difference of outcome measure (MIREDIF), Standard Derivation (SD), Number of cases (N)

#### Evaluation of cost-effectiveness of OPUS YOUNG

The majority of first episodes of psychosis occur in adolescence or young adulthood, and it is important to detect and treat these early as delayed treatments can lead to poor clinical and social outcomes, with potential consequences over the lifetime for the individual and the society. Despite increased implementation costs, investments in EIS for young adults have shown to be cost-effective in OPUS due to lower psychiatric health care costs and better outcome [30]. To assess the cost-effectiveness of the OPUS YOUNG intervention, we will conduct an economic evaluation of the trial adopting a public-sector perspective. The cost-effectiveness analysis compares differences in costs and outcome between the intervention group and standard treatment by calculating the incremental cost-effectiveness ratio [127]. The time horizon of the economic evaluation will be 2.5 years. Outcome measures and cost data will be based on collected research and clinical data combined with register data [30].

#### Evaluation of psycho-educative siblings' groups

In a qualitative-design we will explore siblings' perceptions of being a sibling to a brother or sister with a FEP and identify factors important for siblings to benefit from the psycho-educative siblings' group. We will invite siblings to participate in an individual, semi-structured interview exploring their experiences of being siblings to a brother or sister with FEP using a descriptive phenomenological approach to gain an in-depth understanding of the lived experiences of siblings.

## **Data-management**

The assessors will enter data directly into a database REDCap via an online Case Report Form (CRF). A data manager will ensure that all variables are properly defined with variable and value labels. Algorithms will be kept in special files. Data will be exported to relevant software packages: (SPSS, SAS, Stata, R.). All data will be examined carefully in order to identify errors in data entry.

#### Statistical analyses

The analyses will be according to intention-to-treat with two-sided tests. Missing data will be handled by multiple imputations. The primary outcome measure, as other continuous outcome measures, will be analysed with mixed model analysis with repeated measurements with unstructured variance matrix, using the mixed model command in SPSS. This approach assumes that the distribution of missing data can be estimated from the information from previous assessments and from information about other participant cases in the database. The condition for using this method is the assumption that data are missing at random or missing completely at random when taking into consideration the information extracted from baseline assessments and information about the other participants in the database. In this model, baseline values of the scales are included. All tests will be two-tailed. The threshold for the significance level will be set at p<0.05. For evaluation of the dichotomous outcome measures, we will use multiple multivariate imputations, using all other covariates to impute a distribution of missing values. The dichotomous outcomes will be analysed with logistic regression analyses. Variables included as covariates will be the same as those included in analyses of continuous measures. Similar to the repeated measurement, the condition for using multiple imputations requires that data are missing at random or missing completely at random, when taking into consideration the information extracted from baseline interviews and information about the other patients in the database. Analysis will be based on intention-to-treat principles. Data from all patients will be included in the group to which random assignment is made, regardless of intervention received.

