Suicidal behaviour	Self-reported suicidal ideation and behaviour	Ι		X	X	X	X
School adherence	Days in school/education/employment (%)	R/I		X	Х	Х	Х
Substance abuse	TEM	Ι		X	X	X	X
Somatic Health	Clinical assessment  , laboratory tests  , ECG	ME		X	X	X	X
Medication side-effects	UKU	Ι		X	X	X	X
Medication compliance	Self-reported use of antipsychotic medication I			X	X	Χ	X
User perspectives on	Semi-structured interview I					X	
trans-sectorial activities							
Assessment of parents or	legal caretakers		Ass	essm	ent 1	time,	
			moi	nths			
Topic:	Instrument/measure:	Adm*	A*	0	12	24	30
Parent information on child	1:						
Primary and comorbid	K-SADS-PL (full)		Х		X	X	
diagnoses							
Executive functioning	BRIEF-2	Q		X		X	

Negative effects of	NEQ Q					X	
psychological treatment							
School adherence	Days in school/education/employment (%) Q				X	X	X
Duration of untreated	Duration of untreated psychosis (incl. patient	Q		X			
psychosis	referral process)						
Genetic predispositions	Genetic predispositions	Q		X			
Information on parents/far	nily:						·
Demographics	Demographic information	Q		X	X	X	X
Parental Stress Scale	Stress Scale PSS Q			X	X	Χ	X
Family Function	FAD	Q		X		Χ	X
Self-efficacy	GSE	Q		X	X	Χ	X
Client satisfaction	CSQ	Q			X	Х	
User perspectives on	Semi-structured interview	Ι				X	
trans-sectorial activities							
Clinician assessment			Ass	essn	nent 1	time,	
			months				
Topic:	Instrument/measure:	Adm*	A*	0	12	24	30
Working alliance	WAI					X	
User perspectives on	Semi-structured interview					X	
trans-sectorial activities							
Municipal collaborators			Ass	essn	nent 1	time,	,
			moi	nths			
Торіс:	Instrument/measure:	Adm*	A*	0	12	24	30
User perspectives on	Semi-structured interview					X	

 trans-sectorial activities
 Image: Image:

research data if informed consent is obtained.  $4DM^* = Administration modus: I=interview. O=questionnaire. R=registration. ME=will be obtained from the medical journal. IR=$ 

*ADM*\* = Administration modus: I=interview, Q=questionnaire, R=registration, ME=will be obtained from the medical journal, IR= Interviewer-Rated.

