#### Randomization

After baseline assessment the participants will be randomized 1:1 to either the experimental treatment (OPUS YOUNG intervention) or standard treatment (TAU). Randomization of the

participant will be centralised and computerised with concealed randomization sequence carried out by the database system used in the Capital Region of Denmark (REDCap) [61]. The randomization concealment mechanism is performed by a computer algorithm saved in REDCap [61]. Randomization cannot be influenced by persons, and block size will be unknown for investigators and clinicians. To optimize the comparability between treatment groups, randomization will be stratified by the two factors: *age* (12-14 years and 15-17 years) and for the main outcome, *PSP* (score 1-44 and score 45-100).

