#### Hierarchy of outcome measures

#### **Primary outcome**

The primary outcome is change in the estimate of the adolescent's social function, measured with Personal and Social Performance Scale (PSP) [43]. PSP provides a global score on a scale from 1-100, with lower scores indicating lower social functioning, as well as scores on four subdomains (Socially useful activities, Personal and social relationships, Self-care, and Disturbing and aggressive behaviour) on a scale 6-point Likert scale. The scoring of PSP is based on all available information and concerns the patient's daily level of functioning in the family, in school, and during leisure time during the past month. Researchers will interview the participants prior to the scoring of PSP using a semi structured interview guide suitable for children and adolescents, developed by the OPUS YOUNG research team. The final PSP-score will be determined using consensus rating, by which the rater will discuss the PSP score with an experienced user of PSP (the co-PI of the OPUS YOUNG study) and/or a senior consultant and other researchers from the research team. Prior to the initiating the OPUS YOUNG study, we will conduct a pilot-study to ensure that the assessors have a high level of inter-rater reliability with ICC values for the primary outcome measure of at least 0.70, prior to working as assessors in the trial (ICC is calculated in SPSS using two-way mixed models for absolute agreement on single measures). Assessors at entry and at the follow-up interviews will be independent and blind to treatment allocation. Patients will be instructed to maximize efforts to keep their treatment allocation unknown for the investigator.

*Secondary outcome measures*: Positive symptoms, negative symptoms, and disorganized symptoms (SAPS and SANS); client satisfaction (CSQ); and quality of life (KIDSCREEN-10).

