#### Exploratory outcomes:

Affective symptoms (YMRS, HAM-6); global psychopathology (CGI-S, CGI-I); duration of untreated psychosis (IRAOS); global cognitive functioning (BACS total score); social cognition (Hinting Task and EIMT); general self-efficacy (GSE); patient and clinician rated treatment alliance (WAI); negative effects of psychological treatment (NEQ); school adherence; parental stress (PSS); family function (FAD); quality-adjusted life year (CHU9D and EQ5D); executive functioning (BRIEF); socially useful activities, personal and social relationships, self-care, disturbing and aggressive behaviours (PSP subscales); use of psychopharmacological treatment; substance abuse; and the use of psychiatric and social services.

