#### The specific hypotheses examined are:

- *The primary hypothesis:* 2 years OPUS YOUNG is superior to 2 years TAU (CAMHS or CAMHS+AMHS) examined in all patients aged 12.00 to 17.99 years at inclusion.
- *Planned sensitivity analysis 1*: 1-year OPUS YOUNG vs. 1-year TAU CAMHS in patients ages 12.00 to 16.99 years at inclusion (hence, the patients in this study sample do not turn 18 years during the trial and are solely treated in CAMHS).
- Planned sensitivity analysis 2: 2-years OPUS YOUNG vs. 2-years TAU CAMHS in patients aged 12.00 to 15.99 years at inclusion (hence, the patients in this study sample do not turn 18 years during the trial and are solely treated in CAMHS for the entire intervention period of 2 years).
- Planned sensitivity analysis 3: 2-years OPUS YOUNG vs. 2-years TAU CAMHS + AMHS in patients aged 17.00 to 17.99 years at inclusion (hence, all patients in the TAU group will have undergone transition from CAMHS to AMHS, while the patients in the OPUS YOUNG group will receive OPUS YOUNG treatment for the entire 2 years of intervention.

Due to expected lower sample size in the three planned sensitivity analysis, we do not aim to show statistical superiority of OPUS YOUNG over TAU in these analyses but will examine possible differences by comparing effect sizes.

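### The stated covariate rule does not cover the age stratum in any model, nor clearly baseline PSP outside the PSP model, so the analysis is valid but slightly conservative

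*Protocol*

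**What the plan says.** Protocol, Randomization: "To optimize the comparability between treatment groups, randomization will be stratified by the two factors" age (12-14 and 15-17 years) and PSP (1-44 and 45-100).

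Protocol, Statistical analyses: "The primary outcome measure, as other continuous outcome measures, will be analysed with mixed model analysis" for repeated measurements with an unstructured variance matrix. On covariates the section adds only "In this model, baseline values of the scales are included". For logistic regression it says "Variables included as covariates will be the same as those included in analyses of continuous measures" and gives no list. Neither age nor the stratification factors are named for any model.

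Protocol, Hierarchy of outcome measures, lists among the secondary outcomes "client satisfaction (CSQ); and quality of life (KIDSCREEN-10"). Table 1 schedules CSQ at months 12 and 24 only.

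Protocol, specific hypotheses: sensitivity analysis 3 is run "in patients aged 17.00 to 17.99 years at inclusion".

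**The concern.** Stratified allocation makes the arms more alike on the stratification factors than chance would. The treatment estimate then varies less than an analysis ignoring those factors assumes. If the factors relate to the outcome and the model leaves them out, the reported standard error is too large, the test runs below its nominal 5%, and some of the precision that stratification bought is lost.

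Here the protocol does state covariate content, applies it to all continuous outcomes and reuses it for logistic models. Followed as written, that content has two gaps:

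- **Age stratum.** It is not a scale score, so the sentence does not reach it in any model.
- **Baseline PSP.** It is in the PSP model. For SAPS, SANS and KIDSCREEN-10, it is in only if the plural means that the baselines of all scales enter every model. If it means each outcome's own baseline, the PSP stratum is absent from those models.

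A smaller point of wording is that CSQ has no month-0 value, so an own-baseline rule supplies no covariate for it. What is at stake is a little precision and an avoidable later choice, not the validity of the result.

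**Working it through.** **The plan's own figure.** N = 4 × (1.960 + 1.282)² × (13/5)² = 284.1, or 42 × 6.76 = 283.9 with the rounded constant. The stated 284 reproduces, and power at 142 per arm is 90.0%. That calculation compares two means without covariates, so the point does not touch it.

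**Inputs from the protocol.** 142 per arm; two-sided alpha 5%; difference and SD of 5 and 13 (PSP), 0.4 and 1.2 (SANS), 5 and 10 (KIDSCREEN-10), 3.09 and 4.45 (CSQ).

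**Assumed inputs, not in the protocol.** Correlation r between baseline and endpoint: 0.5, range 0.3 to 0.7. Share R² of the remaining variance explained by the omitted strata: 2%, 5%, 10%. Share of patients aged 15-17: 70%.

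**Formulas.** With own baseline in the model, SE = SD × √(1 − r²) × √(2/142). Put k = √(1 − R²). After stratified allocation the true standard error is SE × k, while a model without the strata reports SE. Hence:

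- alpha without strata = 2 × [1 − Φ(1.96/k)]
- power without strata = Φ((d/SE − 1.96)/k)
- power with strata = Φ(d/(SE × k) − 1.96)

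**Alpha.** k = 0.990, 0.975, 0.949 gives critical values 1.980, 2.011, 2.066 and alpha 4.77%, 4.43%, 3.88%.

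**Power at r = 0.5.** For PSP, SE = 13 × 0.866 × 0.1187 = 1.336 and d/SE = 3.742. For SANS, SE = 0.1233 and d/SE = 3.243.

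| Outcome | R² | Without strata | With strata | Loss (points) |
|---|---|---|---|---|
| PSP | 2% | 96.41 | 96.56 | 0.15 |
| PSP | 5% | 96.63 | 96.99 | 0.36 |
| PSP | 10% | 96.99 | 97.64 | 0.66 |
| SANS | 2% | 90.26 | 90.59 | 0.34 |
| SANS | 5% | 90.60 | 91.43 | 0.83 |
| SANS | 10% | 91.19 | 92.77 | 1.58 |

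The losses are computed before rounding. KIDSCREEN-10 loses at most 0.03 points. Over r = 0.3 to 0.7 the loss runs from 0.03 to 1.24 points for PSP and from 0.11 to 2.33 for SANS. For CSQ without any baseline term, d/SE = 3.09/0.528 = 5.85, so power is above 99.9% with or without the strata.

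**How plausible is each R² for PSP?** Baseline PSP is already in that model, so essentially only age is missing. The age-group difference needed beyond baseline, in SD units, is g = √[R² × 0.75 / ((1 − R²) × 0.21)], where 0.75 = 1 − r² and 0.21 = 0.7 × 0.3. This gives 0.27, 0.43 and 0.63 SD, or 3.5, 5.6 and 8.2 PSP points. The last exceeds the minimal relevant difference of 5, so the lower R² values are likelier.

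**Simulation for PSP.** 10,000 trials per cell, N = 284, blocks of 4 (assumed), baseline PSP in both models, without versus with age stratum. For an age shift of 3.25 points, alpha is 4.8% versus 5.0% and power 96.0% versus 96.2%. For 6.5 points, alpha is 4.3% versus 5.0% and power 95.7% versus 96.4%. The Monte Carlo standard error is about 0.2 points, so the smaller power loss is of the size of the simulation error.

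**The case against.** The strongest reply is that a full covariate list is ordinary SAP content, and the sentence does not claim to be complete. It also follows text on missing data, so it may only mean that month-0 values are part of the repeated-measures data. Nothing in the protocol excludes age.

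Part of this stands: the sentence may be incomplete rather than wrong, and an SAP could supply the missing terms. It does not remove the point. The section states which values enter the model, applies this to all continuous outcomes and carries the covariates over to the logistic models. Such a statement should fit the protocol's own randomisation, and no reading of it covers age.

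The reply is right that the gain is small and that the assumed inputs drive its size. It is also right about CSQ. A reader might infer that CSQ cannot be analysed as planned. The documents do not support that: a model for months 12 and 24 can be fitted without a baseline, and if the baselines of all scales enter every model, CSQ has covariates. Nor does anything rest on the logistic models, since the protocol's outcome lists designate no outcome as dichotomous.

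**Conclusion.** The point holds as a modest, concrete improvement. The stated covariates omit the age stratum from every model and, on the own-baseline reading, omit baseline PSP from the models for outcomes other than PSP.

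A reader might infer that the primary test is invalid, that type I error is inflated or that the trial is too small. None of these follows. Leaving out stratification factors makes the test conservative, leaves the treatment effect on continuous outcomes unbiased and does not alter N = 284. The size rests on the assumed R² and r. For PSP the lower end of the range is the more likely. The SANS figures apply in full only if baseline PSP is left out of that model along with age. The CSQ conclusion is unaffected.

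**What to change.** In Statistical analyses, replace the covariate sentence with:

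> All models include age stratum (12-14/15-17) and baseline PSP score as fixed effects, plus the outcome's own month-0 value where one is scheduled. The age term is omitted in sensitivity analysis 3, where all patients are in one age stratum.

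For PSP, the baseline score and the own month-0 value are the same term and enter once. As a minor clarification, the wording also settles CSQ, which is then adjusted for age stratum and baseline PSP only.

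The cost is at most two degrees of freedom per model. Both variables are recorded before randomisation, so data collection and sample size do not change. If a logistic model is used, its odds ratio is conditional on these covariates and should be reported as such.
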